7.5.9. Clinical Laboratory Evaluations

Blood and urine samples will be collected for hematology, clinical chemistry and urinalysis as described in the protocol, at time points described in the protocol.

Numeric hematology and clinical chemistry laboratory results will be presented using SI units.

All individual laboratory values will be listed with occurrence of values above and below the normal reference range.

Pregnancy test results will be reported in a separate listing.

Hematology and clinical chemistry laboratory values and change from Screening values will be summarized by study visit window.

For those parameters that have CTCAEv3 criteria, shift tables showing changes in CTCAEv3 grade from baseline to the worst grade post Screening will be presented. Parameters with CTCAEv3 criteria defined bi-directionally will have low value abnormalities represented by a negative sign so that they may be differentiated from high value abnormalities. If the CTCAEv3 criteria are unidirectional the negative sign will not be used even if the criteria were defined to flag low value abnormalities.

An additional indicator of drug-induced liver injury will be presented. A listing will be prepared of all subjects who received a dose of study drug and met Hy's Law following dosing. The criteria for Hy's Law are either AST or ALT > 3X the upper limit of normal (ULN) coincident with ALP < 2XULN and total bilirubin > 2XULN.^[4]

The number of subjects with post-Screening CTC grade 3/4 labs will be summarized.

Additional listings will be provided for four hematological parameters: WBC, HGB, absolute neutrophils, and platelets. These listings will provide, by therapeutic dose, screening values, nadir values/grade, time to nadir value, and time to recovery (grade ≤1) post nadir value. Figures will be produced by subject for absolute neutrophils and platelets.

Renal function testing was performed for the subjects. For most subjects either glomerular filtration rate (GFR) or serum creatinine clearance was reported. For some subjects, only 24-hour urine creatinine was reported and will be used to evaluate renal function if either GFR or serum creatinine clearance was not reported. If the urine creatinine clearance values were reported in units other than mL/min or cannot be converted into units of volume/time, then those records will be treated as unevaluable (missing).

An estimated creatinine clearance may be calculated based on serum creatinine, urine creatinine and urine volume. Serum creatinine values within 7 days prior to urine collection may be combined with the urinalysis parameters. Renal function based on estimated creatinine clearance values will be categorized as normal (≥90 ml/min), mild decrease in GFR (60-89 ml/min), moderate decrease in GFR (30-59 ml/min), severe decrease in GFR (15-29 ml/min) and end stage renal disease (<15 ml/min not on dialysis or requiring dialysis). A shift table of creatinine clearance from Baseline to the 12-month endpoint will be provided.

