11.5.4 Laboratory Evaluations

Blood and urine samples will be collected for hematology, clinical chemistry and urinalysis as described in Table 2, at the following time points:

- at the screening/baseline period
- within 24 hours prior to the imaging and first therapeutic Ultratrace iobenguane I 131 infusion
- within 48 hours prior to the second therapeutic Ultratrace iobenguane I 131 infusion
- weekly starting with Week 2 until 24 weeks following administration of the first Therapeutic Dose of Ultratrace iobenguane I 131 and continued for at least 12 weeks following administration of the second Therapeutic Dose. Note: the first blood sample following each therapeutic Ultratrace iobenguane I 131 infusion is not required until 2 weeks post-infusion
- The blood draw and urine collection do not need to be repeated at Month 3 if the visit is within a week of the Week 12, Week 13, Week 14 or Week 15 blood draw
- The blood draw and urine collection do not need to be repeated at Month 6 if the visit is within a week of the Week 24 visit, Week 25, Week 26, Week 27, Week 28, Week 29 blood draw. (Week 25, Week 26, Week 27, Week 28, Week 29 blood draws are only performed if the second therapeutic dose is delayed)
- Monthly, 7 through 12 months after the first Therapeutic Dose of Ultratrace iobenguane I 131.
- TSH, T3 and T4 analysis will only be performed at screening/baseline and at the Month 12 Efficacy Visit

Hematology	Clinical Chemistry		Urinalysis
Hematocrit	Sodium	AST/SGOT	pН
Hemoglobin	Potassium	ALT/SGPT	Specific gravity
RBC count	Chloride	Alkaline Phosphatase	Protein
WBC count	Glucose	Cholesterol	Glucose
Differential WBC count	Urea nitrogen	Total protein	Ketones
Platelet count	Creatinine	Albumin	Blood
PT or INR	Total bilirubin	LDL	WBC/HPF
	Triglycerides	HDL	RBC/HPF
	Calcium	Phosphorus	Crystals
	TSH*	T3/T4*	

TABLE 2: LABORATORY ANALYTES

*TSH, T3 and T4 analysis will only be performed at screening/baseline and at the Month 12 Efficacy Visit.

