Table 14.2.4.1	EORTC QLQ-C30 Global Health Status/Quality of Life (Population: Full Analysis Set)
Table 14.2.4.2	EORTC QLQ-C30 Functional Scales (Population: Full Analysis Set)
Table 14.2.4.3	EORTC QLQ-C30 Symptom Scales (Population: Full Analysis Set)
Table 14.2.5A	NIH Pheochromocytoma Symptoms QOL Questionnaire: Pre Amendment 2 (Population: Full Analysis Set)
Table 14.2.5B	NIH Pheochromocytoma Symptoms QOL Questionnaire: Amendment 2 (Population: Full Analysis Set)
Table 14.2.6	Karnofsky Performance Status (Population: Full Analysis Set)
Table 14.2.7	Tumor Pain Medication Shift Table (Population: Full Analysis Set)

Table 14.2.8.1	Overall Survival (Population: Full Analysis Set)
Table 14.2.8.2	Overall Survival by Primary Endpoint Status (Population: Full Analysis Set)
Table 14.3.1.1	Treatment-Emergent Adverse Events (Population: Safety)
Table 14.3.1.1.1	Treatment-Emergent Adverse Events with Start Dates after Week 15 Following the Last Therapeutic Dose (Population: Safety)
Table 14.3.1.1.2	Treatment-Emergent Adverse Events with Start Dates after the Start of a New Anticancer Therapy but Prior to Week 15 for Subjects who Withdrew due to New Anticancer Treatment (Population: Safety)
Table 14.3.1.2	Treatment-Emergent Adverse Events by Grade (Population: Safety)
Table 14.3.1.3	Treatment-Emergent Serious Adverse Events (Population: Safety)
Table 14.3.1.4	Hematologic Serious or Grade 3/4 Adverse Events (Population: Safety)
Table 14.3.1.5	Grade 3/4 Adverse Events (Population: Safety)
Table 14.3.1.6	Adverse Events of Special Interest (AESI) (Population: Safety)
Table 14.3.2.1	Listing of Deaths During 12 Month Assessment Period (Population: Safety)
Table 14.3.2.2	Listing of Serious Adverse Events (Population: Safety)
Table 14.3.2.3	Listing of Adverse Events Leading to Drug Withdrawal (Population: Safety)
Table 14.3.2.4	Listing of Adverse Events of Special Interest (AESI) (Population: Safety)
Table 14.3.4.1.1	Change from Baseline in Hematology (Population: Safety)
Table 14.3.4.1.2	Change from Baseline in Chemistry (Population: Safety)
Table 14.3.4.1.3	Change from Baseline in Urinalysis Results (Population: Safety)
Table 14.3.4.1.4	Shifts in CTC Grade for Laboratory Parameters with Uni-Directional Criteria (Population: Safety)
Table 14.3.4.1.5	Shifts in CTC Grade for Laboratory Parameters with Bi-directional Criteria
Table 14.3.4.1.6	Incidence Rate of Post First Therapeutic Dose CTC Grade 3/4 Laboratory Values (Population: Full Analysis Set)

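### For laboratory parameters graded in both directions, the SAP's shift to one signed worst grade has no rule for a subject with both low and high abnormalities, so one direction may be under-counted in Table 14.3.4.1.5

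*SAP*

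**What the plan says.** SAP 7.5.9 states that, for parameters with CTCAE version 3 criteria, "shift tables showing changes in CTCAEv3 grade from baseline to the worst grade post Screening will be presented". On those graded in both directions it adds: "Parameters with CTCAEv3 criteria defined bi-directionally will have low value abnormalities represented by a negative sign". The stated purpose is to tell the two directions apart. Where the criteria run in one direction only, no sign is used, even if that direction is low.

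The list of planned outputs (SAP section 11) has one shift table for one-directional criteria (14.3.4.1.4) and one for two-directional criteria (14.3.4.1.5, "Shifts in CTC Grade for Laboratory Parameters with Bi-directional Criteria"). The latter appears by title only, with no shell or row layout.

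Three other outputs in 7.5.9 bear on the same data:

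- Listings: "All individual laboratory values will be listed with occurrence of values above and below the normal reference range".
- A count of severe grades: "The number of subjects with post-Screening CTC grade 3/4 labs will be summarized". Whether it is split by direction is not stated.
- Nadirs: "Additional listings will be provided for four hematological parameters: WBC, HGB, absolute neutrophils, and platelets". These include the nadir grade for each therapeutic dose.

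Protocol section 13.3.3.1 asks for tables of shifts from baseline for graded laboratory results and gives no rule on direction.

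**The concern.** A low and a high value of the same analyte are different harms, and a toxicity grade orders severity only within one direction. Once the two directions are joined by a sign, worst has no defined meaning. It could be the largest number, in which case +1 outranks -4. It could be the largest absolute value, in which case a -2 is hidden behind a +3 and a -2/+2 tie has no answer. Either way, a table that holds one grade per subject and parameter drops one of the two events.

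Sampling is dense. Protocol section 11.5.4 schedules laboratory tests "weekly starting with Week 2 until 24 weeks following administration of the first Therapeutic Dose", followed by monthly draws in Months 7 to 12, so a subject has many chances to leave the range on either side. At stake are the accuracy of one safety table and its reproducibility, because two programmers could build different tables from the same text.

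**Working it through.** **1. Reading the text.** The documents give no figure on this point, so there is none to reproduce. Two features of the SAP point to one signed grade per subject and parameter.

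- The worst grade is singular.
- A sign is needed only if both directions share a scale. With separate low and high rows, the row label would carry the direction, and each two-directional parameter would become two one-directional shifts.

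The SAP does not literally state one grade per subject across directions, and it does not exclude two rows. What can be shown is a missing rule whose natural reading loses information.

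**2. Size if worst means largest absolute grade.** The following assumptions are not in the documents: the worst low and worst high grades are independent across subjects; a share pL has any low grade and a share pH any high grade; and in each direction grades 1 to 4 split 60/25/10/5%.

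- Chance of equal grades, given both directions: 0.60² + 0.25² + 0.10² + 0.05² = 0.435.
- Chance that the high grade is strictly larger, given both: (1 - 0.435)/2 = 0.2825.
- Share of low-abnormal subjects whose low grade is lost: 0.2825 × pH, or (0.2825 + 0.435) × pH = 0.7175 × pH if ties also go to high.
- Expected number of subjects with both: N × pL × pH, with N = 58 (planned) or 75 (approximate enrolment), from SAP section 6.

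| pL = pH | Both, N=58 | Both, N=75 | Low grade lost | Low grade lost, ties to high |
|---|---|---|---|---|
| 10% | 0.6 | 0.75 | 2.8% | 7.2% |
| 20% | 2.3 | 3.0 | 5.7% | 14.3% |
| 40% | 9.3 | 12.0 | 11.3% | 28.7% |

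A grade 3 or 4 low value is displaced by a strictly higher grade only when a -3 meets a +4. At the highest rates and N = 75 the expected count is 75 × 0.40 × 0.40 × 0.10 × 0.05 = 0.06 subjects per parameter. The loss therefore falls almost entirely on grades 1 and 2.

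**3. Upper illustration.** There are 29 scheduled post-dose draws: 23 weekly (Weeks 2 to 24) and 6 monthly. With assumed per-draw chances pl and ph, and draws treated as independent,

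P(both) = 1 - (1-pl)^29 - (1-ph)^29 + (1-pl-ph)^29.

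- pl = ph = 0.01: P(both) = 0.062, P(any low) = 0.253, ratio 25%.
- pl = 0.03, ph = 0.05: P(both) = 0.450, P(any low) = 0.587, ratio 77%.

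The ratio is the share of low-abnormal subjects hidden if any high grade always wins.

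**4. Sensitivity to independence.** Keep the same per-draw rates, but give each subject a normally distributed latent value with within-subject correlation r between draws (r is also assumed).

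| pl, ph | r | P(both) | Low hidden if high always wins |
|---|---|---|---|
| 0.01, 0.01 | 0 | 6.2% | 25% |
| 0.01, 0.01 | 0.3 | 0.4% | 2% |
| 0.01, 0.01 | 0.5 | 0.01% | 0.1% |
| 0.03, 0.05 | 0 | 45% | 77% |
| 0.03, 0.05 | 0.3 | 9.7% | 25% |
| 0.03, 0.05 | 0.5 | 1.4% | 4.8% |
| 0.03, 0.05 | 0.7 | 0.01% | 0.1% |

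The large figures come from treating serial draws in one patient as independent, and they shrink quickly once that is relaxed.

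**5. With separate directions** nothing is lost under any of these assumptions.

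**The case against.** The strongest reply is that the SAP never says one grade is kept across directions. The sign is described as a label to tell low from high, and the table has no shell, so a worst-low and a worst-high row per parameter would comply. That is correct. A reader might infer that the plan expressly discards one direction; the text does not go that far.

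A reader might also infer a large loss, with 6% to 45% of subjects abnormal in both directions and 25% to 77% of low abnormalities hidden. The documents do not support this. The per-draw rates have no source in them, independence of 29 draws is implausible, and the second range also needs +1 to outrank -4, which is not how worst grade is ordinarily understood.

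The third reply is that other outputs show both directions: flagged listings, summaries by visit window, the grade 3/4 count, the nadir listings, and adverse event tables where a laboratory change is reported as an event. This limits the damage but does not remove it. A listing does not give a number of subjects. The nadir listings cover four hematology parameters and no chemistry. The grade 3/4 count leaves out grades 1 and 2 and does not state direction. For chemistry, Table 14.3.4.1.5 is the only planned subject-level summary of laboratory grades that carries direction. The SAP does not list which parameters have two-directional criteria, so the number affected is not known from the documents.

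**Conclusion.** The point holds as a minor gap. SAP 7.5.9 puts both directions on one signed scale, asks for a single worst grade, and gives no rule for subjects with both or for ties. On the natural reading, one direction is under-counted in Table 14.3.4.1.5.

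The size cannot be derived from the documents. Under the assumed rates in step 2 it is a few subjects per parameter at most, mainly at lower grades. Positive within-subject correlation would make it smaller still, so it is probably small. It does not touch the listings, the nadir listings or the primary endpoint, and no test or decision rule depends on the table.

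**What to change.** In SAP 7.5.9, state that for parameters with criteria in both directions the worst post-baseline low grade and the worst post-baseline high grade are derived separately for each subject. Present each as its own shift against the baseline grade in the same direction, so that a subject with both appears in both. Lay out Table 14.3.4.1.5 with a low block and a high block per parameter. The sign and the tie question then fall away.

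The cost is a sentence in the SAP, one extra derived grade per two-directional parameter and a longer table. No new data are needed.

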7.5.10. Vital Signs Measurements

Vital signs (blood pressure, pulse, temperature and respiration) will be collected at the time points listed in the protocol. All vital signs measurements will be provided in listings. The listing will include all measurements recorded during the study, with a column included for origin (e.g., health care provider vs. subject measurement).

Summary statistics of vital signs and the changes from Screening will be presented in the table by visit according to its respective visit window. Pre-dose to post-dose changes for each administration of iobenguane I 131 will also be summarized.

Heart rate and blood pressure measurements are recorded both by healthcare providers and by the subjects, as indicated in the protocol. The results from the healthcare providers at site visits or at the subjects' homes will be combined for each subject for sitting and supine positions and respective visit window as indicated in [Appendix 1](#). This table will exclude blood pressure readings by subjects themselves. The recordings done by the subjects themselves were used to help guide the investigators in management of anti-hypertensive medications, but were not intended to be included in the vital sign data set. The mean values for each subject and time point will be used as the basis of the summaries. Summary statistics for heart rate and blood pressure results and their respective changes from baseline will be prepared.

Subjects who develop changes from Screening or values of potential clinical importance will be tabulated by study visit and overall, and will be flagged in the subject data listings. Criteria will be as follows:

- Systolic BP increase or decrease >20 mmHg
- Diastolic BP increase or decrease >10 mmHg
- Pulse rate increase or decrease >20 bpm
- Temperature >38.0°C or >100.4°F

Vital signs obtained within 24 hours of administration of the study drug will also be flagged if the change in BP or pulse rate specified above occurred compared to the vital signs obtained 30 minutes pre-administration.

By-subject figures for systolic and diastolic BP measurements for sitting and supine positions combined relative to days post first therapeutic infusion, along with antihypertensive medication dose, will be provided as indicated in [Section 7.4.2](#). Two set of figures will be provided: one set will exclude measurements obtained by the subject. The other set will present the measurements obtained by the subjects.

7.5.11. 12-Lead Electrocardiograms

Quantitative parameters of ECGs (heart rate and length of RR-, PR-, QT-, QTcB, QTcF- and QRS-intervals) will be presented. The average of the three 12-lead ECGs acquired pre-Imaging injection will be used as Baseline. Post Baseline quantitative parameters and changes from Baseline will be summarized by study visits and time points:

- Following the Imaging dose at 10± 2 minutes, 15±2 minutes, and 20 ± 2 minutes, and within 15 minutes prior to the second and third Imaging I 131 Scans.
- Within 7 days following each Therapeutic Dose.

Changes from baseline of potential clinical importance will be tabulated by study visit window and will be flagged in the subject data listings. Criteria will be as follows:

- Heart Rate: Increase >20 bpm
Decrease >20 bpm
- PR Interval: Increase >30 msec
Decrease >30 msec
- QRS Width: Increase >16 msec
Decrease >16 msec
- QT, QTcB, QTcF Interval: Increase 31–60 msec
Increase > 60 msec
Decrease 31–60 msec
Decrease >60 msec
> 450 msec - 480 msec
> 480 msec - 500 msec
> 500 msec

Qualitative findings, including evaluation of ST-segments and all abnormalities indicated on the assessments following dosing that were not noted at baseline will be listed.

7.5.12. 24-hour Electrocardiogram Monitoring at Therapeutic Dosing

At the time of therapeutic dosing, 24-hour Holter ECG monitoring is performed. The data from these assessments will be summarized for each dosing period.

ECGs will be summarized including changes from the respective predose baseline values. The baseline values are defined as the average of the two readings obtained prior to dosing for results. The following time points are assessed following each therapeutic dose:

- 2 minutes post dosing
- 10 minutes post dosing
- 1 hour post dosing
- 22 hours post dosing

All analyses listed above in [Section 7.5.11](#) for 12-lead ECG data will be performed for the 24-hour Holter monitoring data at these time points.

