9.2 Study Design Rationale

This is a phase II study to evaluate the efficacy and safety of two Therapeutic Doses (each dose 500 mCi, or 8 mCi/kg for subjects weighing 62.5 kg or less) of Ultratrace iobenguane I 131 in subjects with malignant pheochromocytoma or paraganglioma. Prior clinical studies have investigated the value of carrier-added iobenguane I 131 in treating malignant

pheochromocytoma or paraganglioma.³⁻¹⁸ Carrier–added iobenguane I 131 is approved for use in localization of pheochromocytoma and neuroblastoma.³⁶

Higher specific activity of iobenguane I 131 (i.e., Ultratrace iobenguane I 131) may result in greater tumor uptake of radioactivity. In animal studies, the Ultratrace form of iobenguane I 131 has shown increased uptake by normal tissue expressing norepinephrine transporter (NET) such as the heart. In xenografts, the Ultratrace form demonstrated higher radiopharmaceutical concentration in UVW/NET transfected tumors and in SK-N-BE (2c) neuroblastoma.

Subjects will receive baseline assessments including CT or MR and bone scan imaging. Subjects will be administered a 3 to 6 mCi Imaging Dose of Ultratrace iobenguane I 131 to confirm uptake of the study agent by at least one tumor. Each subject will then receive two Therapeutic Doses (each infusion 500 mCi, or 8 mCi/kg for subjects weighing 62.5 kg or less) of Ultratrace iobenguane I 131 at least three months apart. Within 7 days after each Therapeutic Dose, each subject will have a whole body scan. Pre-infusion safety measurements are to serve as the within-subject control for assessing post-infusion measurements for effects of Ultratrace iobenguane I 131 therapy.

As detailed in Section 9.1 Study Design, efficacy will be assessed through monitoring of use of concomitant medications, analyses of objective tumor response via CT or MR imaging, FDG scans (if available), and analysis of tumor marker levels. Safety will be assessed through analyses of treatment emergent adverse events (TEAEs), as well as baseline and pre- and post-infusion ECGs, physical examinations, vital signs measurements, laboratory measurements (including clinical chemistry, hematology and urinalysis), and human radiation absorbed dose estimates to target lesions and normal organs.

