11.5.13 Vital Signs Measurements

Vital signs (blood pressure, pulse, temperature and respiration) will be collected at the time points listed below.

During Screening Period

Pre-dose: Within 4 hours prior to each administration of Ultratrace iobenguane I 131 (Imaging and Therapeutic)

Post-dose: Within 4 hours after each Ultratrace iobenguane I 131 administration

Both the professional staff (site staff or visiting nurse) and each subject will be obtaining blood pressure measurements for this study. The professional staff (site staff or visiting nurse) will measure heart rate and blood pressure using a manual mercury sphygmomanometer (or other device approved by MIP) at screening/baseline, twice weekly in the first 6 weeks following each therapeutic dose, weekly through Week 24 (at weeks when not collected twice weekly), and monthly at Months 7 through 12 as listed in the Schedule of Procedures (Appendix VII). If the second therapeutic dose is delayed, the twice weekly or weekly blood measurements may occur past Week 24. The twice weekly measurements will occur for at least 6 weeks after the second therapeutic dose and the weekly measurements will continue until at least 12 weeks past the second therapeutic dose. In addition, blood pressure and heart rate will be measured every time antihypertensive therapy is changed. If possible, the same site staff will measure the blood pressure for the subject's duration of the clinical trial. If it is not possible for the same personnel to measure the blood pressure for all determinations, care and accuracy of the blood pressure measurement will be emphasized.

The study subjects will be instructed to measure their blood pressure at least 1-2 times/week at the same time each day [e.g., evening before supper or before bedtime] and preferably no more than 7 days between measurements, from screening/baseline to the 12 month visit (Table 3). Subjects will be provided an Omron blood pressure monitor for blood pressure monitoring. Subjects will be trained by site staff to obtain their blood pressure measurements using the procedure outlined below.

TABLE 3: BLOOD PRESSURE MEASUREMENTS

(Blood pressure measurements should be obtained approximately the same time as baseline values throughout the study)	Screening /Baseline	First 6 weeks following therapeutic dose(s) (dose 1 and dose 2)	Through week 24 (at weeks when not collected twice weekly)	Months 7- 12

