7.1. Visit Windows and Relative Days

The complete list of visit windows used throughout the study is provided in [Appendix 1](#).

For efficacy summary tabulations, the visit windows will be used as they apply to the evaluation schedule for each endpoint. In the case of multiple visits per reporting window, the visit closest to the midpoint of the interval will be used for summary assessments. If there are multiple visits equally distant from the midpoint of a window, then the earlier visit will be used. These windows apply to, tumor response, bone scans, site assessment of disease, and Karnofsky performance status tumor markers.

For safety tabulations, day of measurement is computed relative to date of each dose until the next dose occurs, for example prior to the first therapeutic infusion until the second therapeutic infusion occurs, then relative to the second therapeutic infusion. These windows apply to ECGs, vital signs and labs. The visit windows for each assessment (vital signs, ECGs, laboratory tests) are specified in [Appendix 1](#) as the scheduled evaluations vary by assessment.

ECGs will be obtained and summarized for readings within 15 minutes prior to the second and third imaging scans as well as those obtained within seven days following each therapeutic dose.

Vital signs will be summarized for readings 4 hours prior and 4 hours post each dose.

Laboratory results taken within 24 hours post imaging and first therapeutic dose and 48 hours post second therapeutic dose will be summarized in addition to those visits where the assessment are scheduled.

Relative days:

The following relative days will be computed for subjects:

For all subjects and visit dates, compute SDAY (Study day) as assessment date minus informed consent date + 1.

For subjects with at least one dose and visit dates:

- TDAYDOS1 (Treatment day from 1st dosimetry) as assessment date minus date of first dosimetry dose + 1.
- TDAYDOS2 (Treatment day from 2nd dosimetry) as assessment date minus date of second dosimetry dose + 1 for any subjects who received a second dosimetry dose.
- TDAYTX1 (Treatment day from therapeutic dose 1) as assessment date minus date of first therapeutic dose + 1; missing for subjects with only a dosimetry dose.
- TDAYTX2 (Treatment day from therapeutic dose 2) as assessment date minus date of second therapeutic dose + 1; missing for subjects with only 1 therapeutic dose and also for subjects with only a dosimetry dose.

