5	Symptom Response (NIH Pheochromocytoma Clinical Questionnaire) and EORTC QLQ-30 Questionnaire	Screening / Baseline (Day -28 to Day 0) Note: two assessments are to be performed prior to the first therapeutic dose within this window	Week 3 (Day 15 - Day 21) Week 6 (Day 36 - Day 42) Week 10 (Day 64 - Day 70) Week 12 (Day 78 - Day 84) Week 15 (Day 99 - Day 105) Week 18 (Day 120 - Day 126) Week 22 (Day 148 - Day 154) Month 6 (Day 173 - Day 193) Month 7 (Day 203 - Day 223) Month 8 (Day 233 - Day 253)	

No	End Point	From Imaging Dose 1	From Therapeutic Dose 1	From Therapeutic Dose 2
			Month 9 (Day 264 - Day 284) Month 10 (Day 294 - Day 314) Month 11 (Day 325 - Day 345) Month 12 (Day 355 - Day 375)	
6	Tumor Pain Medication		Month 3 (Day 81 - Day 101) Month 6 (Day 173 - Day 193) Month 9 (Day 264 - Day 284) Month 12 (Day 355 - Day 375)	

Safety Assessments

No	End Point	From Imaging Dose 1	From Therapeutic Dose 1	From Therapeutic Dose 2
1	Vital Signs (pulse, temperature, respiration)	Screening / Baseline (Day -28 to Day 0) Day 1: 4 hours prior Day 1: 4 hours post	Day 1: 4 hours prior Day 1: 4 hours post	Day 1: 4 hours prior Day 1: 4 hours post
2	Vital Signs (body weight)	Day 1: prior to dosing	Day 1: prior to dosing	Day 1: prior to dosing
3	Vital Signs (BP and heart rate by Health Staff and Subject Readings)	Screening / Baseline (Day -28 to Day 0) Day 1: 4 hours prior Day 1: 4 hours post	Day 1: 4 hours prior Day 1: 4 hours post Week 1 (Day 2 - Day 7) 2x week Week 2 (Day 8 - Day 14) 2x week Week 3 (Day 15 - Day 21) 2x week Week 4 (Day 22 - Day 28) 2x week Week 5 (Day 29 - Day 35) 2x week Week 6 (Day 36 - Day 42) 2x week Week 7 (Day 43 - Day 49) Week 8 (Day 50 - Day 56) Week 9 (Day 57 - Day 63) Week 10 (Day 64 - Day 70) Week 11 (Day 71 - Day 77)	Day 1: 4 hours prior Day 1: 4 hours post Week 1 (Day 2 - Day 7) 2x week Week 2 (Day 8 - Day 14) 2x week Week 3 (Day 15 - Day 21) 2x week Week 4 (Day 22 - Day 28) 2x week Week 5 (Day 29 - Day 35) 2x week Week 6 (Day 36 - Day 42) 2x week Week 7 (Day 43 - Day 49) Week 8 (Day 50 - Day 56) Week 9 (Day 57 - Day 63) Week 10 (Day 64 - Day 70) Week 11 (Day 71 - Day 77)

No	End Point	From Imaging Dose 1	From Therapeutic Dose 1	From Therapeutic Dose 2

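### SAP 7.5.10 flags acute blood-pressure and pulse changes against a 30-minute pre-dose reading that nothing schedules; the planned reading may fall anywhere in the 4 hours before dosing

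*SAP*

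**What the plan says.** SAP 7.5.10 has two flags for change in vital signs. The limits are the same for both: more than 20 mmHg systolic, 10 mmHg diastolic or 20 bpm, in either direction.

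- **General flag.** "Subjects who develop changes from Screening or values of potential clinical importance will be tabulated by study visit and overall". For blood pressure and pulse the criteria are changes only; there is no absolute limit.
- **Acute flag.** "Vital signs obtained within 24 hours of administration of the study drug will also be flagged" if those limits are passed "compared to the vital signs obtained 30 minutes pre-administration".

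The schedule for the readings is elsewhere. Protocol 11.5.13 sets the pre-dose reading at "Within 4 hours prior to each administration of Ultratrace iobenguane I 131" (imaging and therapeutic) and the post-dose reading at "Within 4 hours after each Ultratrace iobenguane I 131 administration". SAP 7.1 follows the same timing: "Vital signs will be summarized for readings 4 hours prior and 4 hours post each dose". SAP Appendix 1 lists time points 4 hours before and 4 hours after each dose. It then lists blood pressure and heart rate after each therapeutic dose as "Week 1 (Day 2 - Day 7) 2x week".

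Protocol 9.2 adds a general principle: "Pre-infusion safety measurements are to serve as the within-subject control for assessing post-infusion measurements".

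**The concern.** The acute flag names a reference that neither document asks sites to collect. A site can follow the protocol exactly, take vital signs two hours before the infusion, and leave the flag with nothing to compare against. The programmer must then either leave the subject unflagged or choose a substitute that the SAP does not name. The first course undercounts acute changes; the second is an unplanned choice. This can happen at every administration, imaging dose included.

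A smaller question concerns what happens after 24 hours. The acute flag stops there, and later readings are flagged only against Screening. At dose 1 Screening is a recent reading. At dose 2 it predates the first therapeutic dose and any medication change that followed. Protocol 11.5.12 foresees that blood pressure may fall or normalize after therapy. Change from Screening and change from the dose 2 pre-dose reading can then differ. At stake is the accuracy of a descriptive safety table.

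**Working it through.** The plan gives no figure to reproduce. The main check compares texts; the arithmetic below gives only the size.

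**1. Reference time, side by side**

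| Place | Pre-dose reading |
|---|---|
| Protocol 11.5.13 | any time in the 4 hours before dosing |
| SAP 7.1 and Appendix 1 | 4 hours prior |
| SAP 7.5.10, acute flag | 30 minutes before |

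A 30-minute reading is allowed by the schedule but not required. On the lenient interpretation (any reading in the last 30 minutes counts), the share of administrations with a usable reference is:

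- readings spread evenly over 4 hours (assumed): 0.5 / 4 = 12.5%, so 87.5% have none;
- readings spread evenly over the last hour (assumed): 0.5 / 1 = 50%;
- all readings in the last 30 minutes: 100%, and the problem disappears.

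**2. Age of Screening at dose 2 (secondary point)**

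Inputs: Screening up to 28 days before the imaging dose (SAP Appendix 1); imaging dose up to 30 days before dose 1 (Protocol 10.1); dose 2 at least 12 weeks (Protocol 9.3) and at most 24 weeks (Protocol 10.2) after dose 1.

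- Minimum: 12 weeks, plus however long Screening preceded dose 1.
- Maximum: 28 + 30 + 168 = 226 days = 32.3 weeks.

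**3. What an old reference does to the flag**

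Let d be Screening minus the dose 2 pre-dose reading, in mmHg. A rise from pre-dose must exceed 20 + d systolic or 10 + d diastolic to be flagged against Screening. The documents do not give d; the range -10 to +20 is assumed. Protocol 11.5.12 mentions a fall of 20-30 mmHg as an occasion to consider less medication, so d = 20 is a case the protocol names, not a predicted mean.

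The last column is the probability that a true +30 mmHg systolic rise is flagged on one reading. It uses P(N(30 - d, SD) > 20) with an assumed SD of change of 8-12 mmHg.

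| d | Rise needed, systolic / diastolic | Flag probability vs Screening |
|---|---|---|
| -10 | 10 / 0 | 0.95-0.99 |
| 0 | 20 / 10 | 0.80-0.89 |
| 10 | 30 / 20 | 0.50 |
| 20 | 40 / 30 | 0.11-0.20 |

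Against the pre-dose reading the probability is 0.80-0.89 whatever d is. With no true rise, a systolic increase flag has probability 0.01-0.05 against pre-dose, but 0.11-0.20 against Screening at d = -10. The error can go either way.

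**4. What an extended flag would cost**

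Take two readings per dose, no true change, and an assumed correlation of 0.5. The probability that at least one reading passes the limit in either direction is:

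- systolic >20: 0.02-0.17 at SD 8-12;
- diastolic >10: 0.17 at SD 6, and about 0.35-0.6 at SD 8-12.

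Two readings in Days 2-7 can also both miss 48-72 hours (Days 3-4, with dosing on Day 1). If all day pairs are equally likely, 6 of 15 miss: 0.40. If readings are at least 3 days apart, 3 of 6 miss: 0.50.

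**The case against.** On the 30-minute reference there is little to argue. A reading at 30 minutes lies inside the 4-hour window, and a sensible programmer would probably use the scheduled one. But the SAP does not say so, and SAP 7.1 uses the 4-hour window for the same vital signs.

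On Days 2-7 the opposing case is strong. A reader might infer that flagging against Screening at dose 2 breaches Protocol 9.2, or that delayed hypertensive reactions would go unseen. The documents support neither.

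- Protocol 9.2 asks for pre-infusion control of post-infusion measurements. It does not require a fresh reference at each dose, and Screening is pre-infusion. Change from Screening also captures the cumulative effect of both doses.
- The SAP generally keeps a study baseline beyond 24 hours. Twelve-lead ECGs taken within 7 days of each therapeutic dose use the pre-imaging baseline (7.5.11), and laboratory changes are from Screening (7.5.9). The dose-specific reference for Holter ECGs (7.5.12) runs only to 22 hours, which matches the acute flag.
- SAP 7.5.10 also summarizes pre-dose to post-dose change for each administration. A Day 2 reading taken less than 24 hours after dosing still gets the acute flag.
- All readings are listed, blood pressure is plotted by subject with medication dose, and Protocol 12.5 has the investigator judge any worsening from pre-dose as a possible adverse event.
- The rises at 2-3 days in Protocol 7.2 (four patients, three of them mild) followed carrier-added product, whose carrier can itself raise blood pressure (Protocol 7.3). They are a reason to look at those days, not a rate for this product.

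The magnitudes for Days 2-7 also rest on assumed d and SD. Cuts in antihypertensive medication may pull d back towards zero. The figures describe single readings, whereas 7.5.10 bases its summaries on mean values, so they do not estimate miscounts in the planned table.

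What stands: the reference mismatch in full; the age of Screening at dose 2 as a limit on interpretation, not as an error in the plan.

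**Conclusion.** The acute flag is wrong as written. Its reference is unscheduled, and applied literally it would undercount acute blood-pressure and pulse changes. The size depends on site timing, which the documents do not give: from no loss, if every pre-dose reading is in the last 30 minutes, to 87.5% of administrations without a reference, if readings are spread evenly over 4 hours.

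The Day 2-7 point is true but secondary. After 24 hours the only blood-pressure flag is change from Screening, 12 to about 32 weeks old at dose 2, and the resulting descriptive counts can be off in either direction. Flagging these readings against pre-dose is a trade-off, because the diastolic limit would produce many noise flags and two readings can still miss 48-72 hours.

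No endpoint, dosing rule or success criterion uses this table.

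**What to change.** **Needed.** In SAP 7.5.10, replace the 30-minute reference with the last vital signs obtained within the 4 hours before that administration. This costs one phrase and needs no new data.

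**Optional.** Add supplementary rows that compare healthcare-provider blood-pressure readings through Day 7 after each therapeutic dose with that same pre-dose reading. Show them by dose and direction, with systolic and diastolic apart, and add a note that the diastolic limit of more than 10 mmHg will flag much ordinary variation. The cost is some table rows and that noise.

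Leave the Screening-based table unchanged.
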